In the FIH study immune responses to both candidates were clearly evident, despite the high number of previously administered doses of IPV and the inability to detect a 4-fold rise in some participants due to baseline titers within 4-fold of the upper limit of quantitation for the assay. Only one participant did not have a seroprotective level of neutralizing antibodies to type 2 poliovirus at baseline (<1:8), and most participants demonstrated seroconversion (4-fold rise in antibody from baseline to 28 days post-vaccination). Median fold-rise in titer was 12.7 for Cohort 1 and 8.0 for Cohort 2.

This study is of major importance for global public health, contributing to the search of an improved OPV2 vaccine with less chance of reversion to neurovirulence.

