10.1.2 Initial Characteristics Data of the Subject Sample

Descriptive statistics will be provided per group and by site for demographic (e.g., age, height, weight, body mass index race, gender) and other initial subject characteristics

(clinical laboratory values, physical examination, medical and surgical history, concomitant diseases, concomitant medications). Descriptive statistics include mean, standard deviation (SD), median, maximum, minimum, and range for continuous variables and the number and percentage in each group for categorical variables.

Unless specified otherwise in the SAP, statistical tests and confidence intervals will be computed using a two-sided 5% significance level.

Prior and concomitant medications will be coded using the current WHO Drug Dictionary. For comparison with the UAM1 study UAM1 data will be recoded if necessary.

10.1.3 *Immunogenicity Data*

For an overview of primary, secondary and exploratory endpoints, see Section 3.

Neutralizing Type 2 Poliovirus Antibody Titers

At each post-vaccination time point where neutralizing antibody titers are obtained:

- Seroprotection rate with 95% CIs will be tabulated by group and site.
- Seroconversion rate with 95% CIs will be tabulated for post-vaccination time points by group and site
- Median of \log_2 antibody titers will be computed along with 95% CIs by group and site
- GMT with accompanying 95% CIs will be computed by group and site
- Plots of the reverse cumulative distribution of antibody titers will be generated by group and site

The primary immunogenicity endpoint, seroprotection after a single dose of each vaccine candidate, will be formally compared to the corresponding endpoint from UAM1 via a non-inferiority test of each of the novel candidates to the UAM1 Sabin 2 control, each using $\alpha = 0.025$ and a non-inferiority margin of 10%.

Secondary endpoints will be compared to corresponding endpoints from UAM1 in the same manner, using $\alpha = 0.025$ and margin = 10% for binary endpoints (seroconversion), and $2/3 \log_2$ for median antibody titer and GMT ratios. GMTS will be estimated with likelihood-based methods to accommodate censoring at assay ULOQ and LLOQ, and ANCOVA methods will be used to address imbalances in baseline immunity.

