10.2 DETERMINATION OF SAMPLE SIZE

Groups 1 through 4:

Sample size is chosen here to mirror that of the historical control study, UAM1. The serotype 2 Day 28 seroprotection rate among OPV-vaccinated individuals is expected to be 95% for subjects receiving a single dose of either investigational vaccine or the type 2 Sabin OPV control vaccine (historical control). 77 evaluable subjects per vaccine group are required to achieve 80% power for a test of non-inferiority to the historical control with a type I error rate of $\alpha = 0.025$ and a non-inferiority margin of 10%. 45 subjects are required to have 90% probability of observing at least one occurrence of an adverse event, when the true adverse event rate is 5%. Allowing for a 10% non-evaluability/dropout rate requires 50 subjects for the safety evaluations. For each vaccine candidate, both 1- and 2-dose groups may be used to assess the Day 28 immunogenicity endpoint, providing 100 subjects for the primary immunogenicity comparison. Therefore, 50 subjects will be allocated to each dose group, to also collect adequate safety data for each group, as defined above.

Groups 5 through 7:

Due to observed transient and asymptomatic elevated values of alanine aminotransferase (ALT), aspartate aminotransferase (AST) and creatine kinase (CK) in the first-in-human phase 1 study, UAM4a, conducted in IPV-vaccinated adults in a contained environment, CK, ALT, AST, GGT, bilirubin and albumin have been designated for further evaluation in this study. Data from OPV-primed individuals in study UAM1 suggest the background rate of spurious elevations with the safe mOPV2 vaccine may be approximately 6%. If the true rate with either candidate vaccine is 4 times the expected rate, 44 subjects per group (each vaccine, plus control) would be required to have 80% power to detect a significant increase in the rate (lower one-sided 95% confidence bound for risk difference > 0) relative to the placebo group. If, upon review of interim safety data, the DSMB agrees that a) despite all reasonable efforts, recruitment has stagnated, and b) sufficient data have accrued to satisfy safety objectives relevant to these groups, group sizes can be truncated.

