Seroprotection rates at baseline will be accompanied by a two-sided Miettinen and Nurminen 95% confidence interval for the difference for Groups 1 & 2 combined as well as Groups 3 & 4 combined vs the UAM1 control (Group 1 & 2 combined). Similarly, comparisons of baseline seroprotection rate between Group 5 vs 7 and Group 6 vs 7 will be conducted. Comparison of baseline GMTs among these same groups will be conducted by computing the GMT ratio and corresponding two-sided 95% confidence interval obtained from modeling the \log_2 NAb titer as a function of group using SAS PROC LIFEREG, as described above. For IPV-vaccinated subjects, this will include a fixed effect for study site, utilizing SAS LSMEANS for pairwise comparisons. For by-site summaries, comparisons will only be available at the site in common between UAM4 and UAM1.

Comparative Analysis

The primary immunogenicity endpoint, seroprotection after a single dose of each vaccine candidate in OPV-vaccinated subjects, will be formally compared to the corresponding endpoint from UAM1 via a non-inferiority test of each of the novel candidates to the UAM1 Sabin 2 control, each using one-sided $\alpha = 0.025$ and a non-inferiority margin of -10%.

Secondary endpoints will be compared to corresponding endpoints from UAM1 in the same manner, using one-sided $\alpha = 0.025$ and considering margins of -10% for binary endpoints (seroconversion), and 2/3 for median antibody titer and GMT ratios. Non-inferiority margins for these secondary endpoints are not selected based on any specific criteria and are simply intended as benchmarks for unpowered comparisons.

In each case, non-inferiority comparisons will be conducted by computing the difference/ratio in endpoint between each candidate vaccine and the UAM1 Sabin 2 control (novel minus comparator), with corresponding two-sided $\alpha = 0.05$ confidence intervals, and comparing the lower confidence limit to the non-inferiority margin. Miettinen and Nurminen confidence intervals will be used for binary comparisons, asymptotic normal-based methods will be used for GMTs as described above using SAS PROC LIFEREG and incorporating a covariate for the baseline \log_2 NAb level, and bootstrap methods will be used for median titers and other continuous endpoints.

Immunogenicity among IPV-vaccinated subjects (Groups 5 through 7) will be summarized descriptively but will not be compared between groups.

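### The primary non-inferiority comparison with the UAM1 historical control is not adjusted for baseline serostatus, and the SAP's baseline checks against UAM1 lead to no action

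*SAP*

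**What the plan says.** Under SAP 6.6.1 (Comparative Analysis), Day 28 seroprotection in OPV-vaccinated subjects is to be "formally compared to the corresponding endpoint from UAM1 via a non-inferiority test of each of the novel candidates" to UAM1 Sabin 2, at one-sided alpha 0.025 "and a non-inferiority margin of -10" percentage points. The method is given in one clause: "Miettinen and Nurminen confidence intervals will be used for binary comparisons". No stratum, covariate or standardisation is named. The same paragraph gives the GMT model a covariate for baseline log2 titre. Protocol 10.1.3 sets out the same primary comparison; its statement that "ANCOVA methods will be used to address imbalances in baseline immunity" stands in the sentence on GMTs.

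Baseline immunity appears in three other places in SAP 6.6.1:

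- The difference in baseline seroprotection between each candidate and UAM1 gets a 95% Miettinen-Nurminen interval, and baseline GMTs get a ratio with interval. No consequence is attached.
- Seroprotection and seroconversion are summarised by baseline serostatus. This is descriptive.
- If post-dose-1 seroprotection differs between the two UAM4 sites, the comparisons are repeated at the site shared with UAM1, and seronegative and seropositive subsets may be examined. The trigger is a difference within UAM4, not between UAM4 and UAM1, and the subset work is optional.

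**The concern.** Subjects were not randomised between UAM4 and UAM1. UAM1 was a single-site study run before OPV2 cessation; UAM4 has two sites. The randomisation rationale in Protocol 4.2 does not extend to the historical control.

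A subject already at 1:8 or above on Day 0 can be expected to remain there on Day 28, so the endpoint depends partly on how many subjects enter seronegative. A baseline difference between the studies then shows up as a vaccine difference. If UAM4 enrols more seronegatives, a candidate equal to Sabin 2 is more likely to fail; if it enrols fewer, an inferior candidate is more likely to pass. The plan recognises this risk for an exploratory endpoint and provides for it there, but not in the one formal test that carries the primary immunogenicity claim.

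**Working it through.** **Inputs from the documents.** Alpha 0.025 one-sided and margin 10 points (SAP 6.6.1, Protocol 10.2). Protocol 10.2 states: "The serotype 2 Day 28 seroprotection rate among OPV-vaccinated individuals is expected to be 95% for subjects receiving a single dose", for candidate and control alike. It also states: "77 evaluable subjects per vaccine group are required to achieve 80% power for a test of non-inferiority to the historical control". 100 subjects are planned per candidate, and 100 in UAM1 (Protocol Appendix 3). Applying the 10% non-evaluability that Protocol 10.2 gives for safety leaves about 90 per study.

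**Step 1: the plan's own figure.** With unpooled variance, n = (1.960 + 0.842)² × 2 × 0.95 × 0.05 / 0.10² = 74.6, so 75 against the stated 77. Power at 77 is Φ(√(77 × 0.01/0.095) - 1.960) = Φ(0.887) = 81.2%. The stated size reproduces to within two subjects. Exact enumeration of the Miettinen-Nurminen rule at 95% v 95% gives 71% power at n = 77, 79% at n = 90 and 83% at n = 100.

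**Step 2: how baseline enters.** Let b be the share seroprotected at baseline (assumed to stay so) and c the share of seronegatives protected at Day 28. The Day 28 rate is b + (1 - b)c. With the same c in both studies, the crude difference is (b in UAM4 - b in UAM1) × (1 - c). The documents give neither b nor c for OPV-vaccinated adults. The range below is assumed, with b in UAM1 set to 1 - 0.05/(1 - c) so that its Day 28 rate is 95%.

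**Step 3: baseline 5 points lower in UAM4, identical vaccine effect, n = 90 per study.**

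| c | b in UAM1 | b in UAM4 | Day 28 rate, UAM4 v UAM1 | Shift (points) | Exact crude power |
|---|---|---|---|---|---|
| 0.3 | 0.929 | 0.879 | 91.5% v 95% | -3.5 | 36% |
| 0.5 | 0.900 | 0.850 | 92.5% v 95% | -2.5 | 48% |
| 0.7 | 0.833 | 0.783 | 93.5% v 95% | -1.5 | 61% |

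Balanced baselines give 79%.

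**Step 4: the other direction.** Suppose the candidate is truly 10 points worse (85% v 95%) but a more favourable UAM4 baseline adds 1.5 or 3 points to its Day 28 rate. The false non-inferiority rate at n = 90 rises from 2.4% to 5.0% or 9.9%. At c = 0.7 these correspond to baseline differences of 1.5/0.3 = 5 and 3/0.3 = 10 points.

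**Step 5: what adjustment recovers.** Simulation of a Miettinen-Nurminen difference stratified by serostatus with Mantel-Haenszel weights, n = 90 per study:

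- 10% seronegative in UAM4 v 5% in UAM1, c = 0.5 (Day 28 rates 95% v 97.5%): crude bias -2.5 points; power 61% crude, 93% stratified.
- Same seronegative shares, c = 0.8: 94% crude, 98% stratified.
- Balanced at 10%, c = 0.5: about 79-80% crude, 86-87% stratified.
- Balanced at 10%, c = 0.9: 99.4% crude, 98.7% stratified.

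With balanced baselines and an overall rate of 95%, the variance ratio (adjusted to crude) is (1 - b)c(1 - c)/(0.95 × 0.05) = c/0.95: 0.32, 0.53 and 0.74 for c = 0.3, 0.5 and 0.7. The precision gain therefore fades as c rises. A standardised difference with Wald-type variance gave 91-99% power over that range, but a stratified score interval gains less, so the variance method must be named.

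**The case against.** The SAP is not blind to baseline. A reader of the study report would see the baseline difference from UAM1 with its interval, the baseline GMT ratio, and the endpoint by serostatus. Core eligibility is matched: age 18 to 50, at least three OPV doses, no polio vaccine within 12 months. No baseline difference between the studies is documented. All of this stands. It narrows the gap to the absence of an adjusted analysis of the primary endpoint and of any rule for what follows if baselines differ.

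A reader might infer that most subjects start at 1:8 or above, because in the Phase 1 study all but one participant did (Protocol 1.3.2). Those participants were IPV-only vaccinated, whereas the primary comparison concerns OPV-vaccinated adults, so the figure does not transfer.

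The results depend on c, and where nearly all seronegatives respond there is little or nothing to gain. That also stands.

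The remedy has limits. At 5% seronegative the stratum holds about 4 subjects per study (90 × 0.05 = 4.5). At 2% it is empty in at least one study about 30% of the time: 0.98⁹⁰ = 0.162, and 1 - (1 - 0.162)² = 0.30. The stratified test can also be conservative: at a true deficit of about 10 points it rejected in 0.4% of runs, against 2.4% for the crude test. These limits call for a sparse-stratum rule; they do not justify leaving the primary comparison unadjusted.

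**Conclusion.** The point holds conditionally. The primary test takes no account of baseline serostatus, and nothing in the plan acts on a baseline difference from UAM1. If there is such a difference, each 5 points of it moves the crude result by 1.5 to 3.5 points of the 10-point margin for c between 0.7 and 0.3. The size rests on assumed b and c, on seropositives staying protected, and on about 90 evaluable subjects per study; the direction does not.

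Two stronger readings are not supported. First, the study is not underpowered on this account: with balanced baselines the crude test has about 79% power at n = 90 and 83% at n = 100, near the stated 80%. Any loss is relative to an adjusted analysis or conditional on an unfavourable imbalance. Second, a reader might infer that the missing adjustment is what lets an inert candidate pass. That is largely low sensitivity of the endpoint. With both studies at 10% seronegative and Sabin 2 protecting half of them, an inert candidate would show 90% v 95% and pass about 22% of the time crude and 23-24% stratified. Adjustment does not cure this, nor does it address differences between the studies other than measured baseline immunity.

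**What to change.** In SAP 6.6.1, pre-specify for both the PP and TVP analyses a risk difference adjusted for baseline serostatus (below 1:8 v at least 1:8). Use either a Miettinen-Nurminen difference stratified with Mantel-Haenszel weights or a standardised difference with its variance method named. Keep one-sided alpha 0.025 and the -10% margin, and report the crude difference beside it. Make it the primary comparison or, at minimum, a named key sensitivity analysis that must agree before non-inferiority is concluded. State what is done when the seronegative stratum is empty or very small in either study. Record the change in SAP section 7, since Protocol 10.1.3 also describes the comparison.

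The cost is SAP wording and one further procedure. Both studies draw Day 0 serum for polio antibodies, and SAP section 2 allows amendment before database lock. The downsides are a possibly small seronegative stratum, a test that can be conservative and, if the adjusted result becomes primary, supportive status for the crude one.

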6.7 Viral Shedding Analyses

Viral shedding analyses will be descriptive in nature and will include hypothesis tests contrasting nOPV2 recipients with mOPV2 recipients as defined below. The total vaccinated population will be used for viral shedding analyses following the first dose, and the per-protocol population will be used for viral shedding analyses following the 2nd dose. As above, post-dose-1 (pre-dose-2) samples will be combined within vaccine candidate and prior vaccination history, where relevant (combined Groups 1 & 2 for each of UAM1 and UAM4, combined Groups 3 & 4 for UAM4).

6.7.1 Exploratory Viral Shedding Endpoints

Throughout, viral shedding analyses will be conducted by group and dose number. The descriptive summaries below will also be computed separately by site. Between-group inferential analyses will additionally be conducted among the site in common between UAM1 and UAM4, for OPV-vaccinated subjects, if the post-dose-1 between-site GMT comparison indicates a significant difference in immunogenicity between sites. The shedding analyses will be conducted considering all available samples, collected at Days 0-10, 14, 21, 28, and 42 following each dose (with day of vaccination defined as Day 0) and additional samples collected, as necessary, to define the end of shedding for participants. All viral shedding data will be listed, including both sample collection and assay results.

Categorical summaries of type 2 viral shedding positivity (positive via PCR) and continuous summaries of viral titers (\log_{10} CCID₅₀/g among both shedders and shedders/non-shedders combined) will be produced by group and by post-vaccination day. Each of these will be augmented with two-sided 95% confidence intervals. The Clopper-Pearson exact method will be used for shedding positivity rate, and the bootstrap method (10,000 replicates, quantile method) will be used for the median \log_{10} viral titers. Subjects who are PCR-negative for viral shedding at a given time point will be assigned the value of 0 for computations involving the \log_{10} CCID₅₀/g, and values PCR positive for type 2 poliovirus but below LLOQ ($2.75 \log_{10}$ CCID₅₀/g) or above ULOQ ($8.25 \log_{10}$ CCID₅₀/g) will be assigned the corresponding value of LLOQ or ULOQ.

For each subject, the extent of viral shedding will be calculated as the area under the curve (using the linear trapezoidal method) of \log_{10} -transformed values of viral concentration in stool samples as determined using quantitative PCR (viral identity) and CCID₅₀ (titer) from samples taken through 28 days following each vaccine dose, and this continuous variable will be summarized. If a subject is missing two consecutive shedding data points among those intended to be tested for this computation due to samples not provided and/or unevaluable samples, the subject will have a missing value. This requirement regarding consecutive missing samples may be relaxed at the analysis stage if sample size for this computation is significantly impacted. Additionally, the Sheding Index Endpoint (SIE) will be computed as the arithmetic mean of \log_{10} CCID₅₀/g obtained from Days 7, 14, 21, and 28. Here, a single missing daily value will lead to a missing

SIE value, although windows of +/- 2 days will be applied to sample availability. If samples are available at both +1 (+2) and -1 (-2), then the mean \log_{10} CCID₅₀/g from these two days will be used for this computation. This will be summarized as a continuous variable using the same methods for daily viral shedding described above.

Additionally, a summary of time-to-shedding-cessation will be prepared using Kaplan-Meier methods. The day of cessation of shedding will be defined as the day of the first sample negative for shedding after which the following two samples are also negative. Summaries will be produced using Kaplan-Meier methods, and will include quartiles and corresponding 95% confidence intervals, as well as the estimated shedding rate at study days 3, 5, 7, 10, 14, 21, and 28 with corresponding 95% confidence intervals. Subjects who are positive for type 2 viral shedding at their last available assessment date with an evaluable stool sample, or who fail to cease shedding prior to a 2nd dose will be right-censored at the last time point they were known to be shedding virus. The time-to-shedding-cessation curves will be displayed graphically, and the comparison of the difference in time to shedding cessation curves between candidate groups in study M4 and corresponding controls subjects from study UAM1 will be conducted by computing the two-sided log-rank p-value.

A comparison of the extent of shedding among OPV-vaccinated subjects to the corresponding control data from study UAM1 will be conducted by computing the difference in viral shedding rate per study day with corresponding two-sided 95% Miettinen and Nurminen confidence intervals for the difference, and augmented with the difference in median viral shedding for the daily shedding values (\log_{10} CCID₅₀/g) as well as the AUC and SIE alongside bootstrap-based (n=10,000 replicates each) two-sided 95% confidence intervals for the difference. A listing will include the computed time-to-shedding-cessation and the corresponding censoring indicator, the AUC, and the SIE values.

Plots of the reverse cumulative distribution of the viral shedding concentrations (by study day) and each aggregate index will be generated.

